• A value of half of the LOQ will be used to calculate descriptive statistics if the datum is reported as "< LOQ SARS-CoV-2 detected".

• A value of half of the limit of detection (LOD) will be used to calculate descriptive statistics if the datum is reported as "No SARS-CoV-2 detected".

Refer to Table 13-3 for more details on the viral load samples LOQ and LOD. Participants with negative viral load at baseline are not included in the viral load analysis.

Any SARS-CoV-2 viral load samples collected on or after the participants are receiving additional COVID-19 treatments (see Table 13-1) will be excluded from the viral load analysis.

For participants who had received IV RDV prior to the enrollment of this study, their viral loads will be excluded from the analysis.

Base 10 logarithm transformation will be used for analyzing SARS-CoV-2 viral load.

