4.3. Protocol Deviations

A by-participant listing will be provided for those participants who did not meet at least 1 eligibility (inclusion or exclusion) criterion, or took prohibited medications from Screening to the Day 30 Follow-up visit, including:

- Investigational agents for COVID-19 with direct antiviral effect including approved HIV protease inhibitors such as lopinavir (LPV)/ ritonavir (RTV), chloroquine, interferon, etc.
- Strong inducers of P-glycoprotein (e.g. rifampin, rifabutin, carbamazepine, phenytoin or herbal medications)

Protocol deviations occurring after participants entered the study are documented during routine monitoring. The number and percentage of participants with important protocol deviations, and the total number of important protocol deviations by deviation category (e.g., eligibility criteria, informed consent) will be summarized by cohort and overall total for the Safety Analysis Set. A by-participant listing will be provided for those participants with important protocol deviations.

5. **BASELINE CHARACTERISTICS**

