Appendix 2. Pediatric Early Warning Score

Appendix 3. Programming Specifications

1) If the age from the Day 1 eCRF is not available, age will be calculated as follows:

Only year is provided for the date of birth (DOB). Use July 1 for the month and day.

- a) AGE (years) is calculated from the number of days between the DOB and Study Day 1,
- b) Use the SAS INTCK function to determine the number of "1st-of-month days" (eg, January 1st, February 1st, March 1st) between DOB and Day 1 (inclusive),
- c) Divide the result in (b) by 12, AGE = the integer of the result in (c), Age for laboratory test reference range will be based on the age at the sample collection date.
- 2) All screened participants refer to all participants who are screened (ie, with non-missing screening date) and have a screening number. For summaries the same participant is counted only once.
- 3) Screen failure participants are the participants who were screened and answered "No" for any inclusion criteria or "Yes" for any exclusion criteria regardless of which version of protocol the participant was consented to.
- 4) Participants in the All Enrolled Analysis Set are defined as participants enrolled into the study. IXRSRAND is the source to determine whether the participants is enrolled (ie, participant with non-missing ENRDTN in the IXRSRAND dataset), and confirmed by the eCRF ENROLL dataset (ie, ENROLLYN = "Yes" in ENROLL dataset).
- 5) Enrolled treatment (ie, TRT01P in ADSL) is derived from IXRSRAND, while actual treatment received (ie, TRT01A in ADSL) is assigned as the enrolled treatment if the participant took at least 1 dose of study drug and assigned as blank if the participant was never dosed.
- 6) In the disposition table, the reasons for premature discontinuation are displayed in the order as they appear on the eCRF.
- 7) Body mass index (BMI)

BMI will be calculated only at baseline as follows:

- BMI = (weight [kg]) / (height [meters]²)

Baseline height and weight will be used for this calculation if available.

8) Details of additional COVID-19 medications are provided in table below.

Drug name	ATC Code	WHODRUG Preferred Term
Chloroquine	P01BA	CHLOROQUINE
Hydroxychloroquine	P01BA	HYDROXYCHLOROQUINE
Lopinavir/ritonavir	J05AR	LOPINAVIR/RITONAVIR
Ribavirin	J05AP	RIBAVIRIN
Bamlanivimab/Etesevimab		BAMLANIVIMAB/ETESEVIMAB
Casirivimab/Imdevimab		CASIRIVIMAB/IMDEVIMAB
Molnupiravir		MOLNUPIRAVIR

Table 13-1.Additional COVID-19 Medications

ATC = anatomical therapeutic chemical

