Additional medications may be included during final review of concomitant medications prior to data finalization.

9)	Grouping on	COVID-19	medications	other than	the study drug
- /					

Table 13-2.Grouping on the COVID-19 Medications other than the Study Drug

Standardized Medication Name	Experimental antiviral	Immune modulator	Anti- inflammatory	AntiViral antibody therapy	Other medication
ANAKINRA	N	Y	Y	N	Ν
AZITHROMYCIN	Y	Y	Y	N	Ν
BETAMETHASONE	N	Y	Y	N	Ν
CLARITHROMYCIN	N	N	Y	N	N
CYCLOBENZAPRINE	N	Ν	N	N	Y
DEXAMETHASONE	N	Y	Y	N	Ν
DEXAMETHASONE SODIUM PHOSPHATE	N	Y	Y	N	N
DIPHENHYDRAMINE; ZINC ACETATE	N	Ν	N	N	Y
ENOXAPARIN	N	N	N	N	Y
ENOXAPARIN SODIUM	N	N	N	N	Y
GANCICLOVIR	Y	N	N	N	N
HYDROCORTISONE	N	Y	Y	N	Ν
HYDROCORTISONE SODIUM SUCCINATE	N	Y	Y	N	N

Standardized Medication Name	Experimental antiviral	Immune modulator	Anti- inflammatory	AntiViral antibody therapy	Other medication
HYDROXYCHLOROQUIN E	Y	Ν	Ν	N	Ν
IMMUNOGLOBULIN G HUMAN	N	Y	N	N	N
IMMUNOGLOBULIN HUMAN NORMAL	N	Y	N	N	Ν
IMMUNOGLOBULINS NOS	N	Y	N	Ν	Ν
LEVOFLOXACIN	N	Ν	Ν	Ν	Y
METHYLPREDNISOLONE	N	Y	Y	Ν	Ν
ONDANSETRON	N	N	N	N	Y
PLASMA	N	Ν	N	Y	Ν
POTASSIUM PHOSPHATE DIBASIC	Y	Y	Y	N	N
POTASSIUM PHOSPHATE DIBASIC;SODIUM PHOSPHATE	Y	Y	Y	Ν	Ν
PREDNISOLONE	N	Y	Y	N	Ν
PREDNISOLONE SODIUM PHOSPHATE	N	Y	Y	N	N
PREDNISONE	N	Y	Y	N	N
REMDESIVIR	N	N	N	N	Y
RITUXIMAB	N	Y	N	Ν	N
TOCILIZUMAB	N	Y	Y	N	N
ZINC	N	Ν	N	N	Y

Additional medications may be included during final review of COVID-19 medications other than the study drug prior to data finalization.

- 10) Graded Laboratory Abnormalities Summary
 - The following labels will be used for laboratory abnormalities and Grade 3 or 4 laboratory abnormalities summary tables and listings:

Battery	Lab Test Label Used in l-labtox Listing	Toxicity Direction	Lab Test Label Used in t-labtox Table
Hematology	Basophils	Increase	Basophils (Increased)
	Eosinophils	Increase	Eosinophils (Increased)
	Hemoglobin	Decrease	Hemoglobin (Decreased)
	Lymphocytes	Decrease	Lymphocytes (Decreased)
	Monocytes	Increase	Monocytes (Increased)
	Neutrophils	Decrease	Neutrophils (Decreased)
	Platelets	Decrease	Platelets (Decreased)
	WBC	Decrease	WBC (Decreased)
Chemistry	Albumin	Decrease	Albumin (Decreased)
	Alkaline Phosphatase	Increase	Alkaline Phosphatase (Increased)
	ALT	Increase	ALT (Increased)
	AST	Increase	AST (Increased)
	Calcium	Decrease	Calcium (Decreased)
	Calcium, Ionized	Decrease	Calcium, Ionized (Decreased)
	Creatine Kinase	Increase	Creatine Kinase (Increased)

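### The Table 13-1 list that triggers exclusion of viral-load samples does not match the antiviral classes the SAP itself assigns in Table 13-2 and Section 4.3

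*SAP*

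**What the plan says.** Section 3.7 sets the rule: "Any SARS-CoV-2 viral load samples collected on or after the participants are receiving additional COVID-19 treatments (see Table 13-1) will be excluded" from the viral-load analysis. It also removes the viral loads of participants who had intravenous remdesivir before enrolment.

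The trigger list is in Appendix 3, item 8, "Table 13-1.Additional COVID-19 Medications". Its seven entries are chloroquine, hydroxychloroquine, lopinavir/ritonavir, ribavirin, "Bamlanivimab/Etesevimab", casirivimab/imdevimab and molnupiravir. A note below it reads: "Additional medications may be included during final review of concomitant medications prior to data finalization". The note gives no criterion for adding an agent.

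Item 9 of the same appendix, "Table 13-2.Grouping on the COVID-19 Medications other than the Study Drug", assigns each medication to one or more of five classes, two of which are experimental antiviral and antiviral antibody therapy. Two of its rows begin "AZITHROMYCIN Y Y Y" and "GANCICLOVIR Y", where the first flag is the experimental antiviral column. Plasma has a single positive flag, under antiviral antibody therapy.

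Section 4.3 lists among prohibited medications: "Investigational agents for COVID-19 with direct antiviral effect including approved HIV protease inhibitors such as lopinavir (LPV)/ ritonavir (RTV), chloroquine, interferon, etc".

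Section 7.4.3 sends the reader to Table 13-1 for both the medication list and the categories, but only Table 13-2 holds categories.

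**The concern.** Antiviral activity of remdesivir is a secondary objective (Section 1.1). It is reported as the change in viral load by cohort and overall, separately for four sample types (Section 6.2.2). There is no comparator arm. Dropping samples once another antiviral is given is meant to keep that agent's effect out of the summary.

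For this to work, agents that the SAP places in one class should be treated alike, and they are not. Samples after a monoclonal antibody pair are dropped, but samples after plasma are kept. Samples after hydroxychloroquine are dropped, but samples after ganciclovir or azithromycin, flagged in the same column, are kept. Of the three agents that Section 4.3 gives as examples of direct antivirals, two trigger exclusion and interferon does not.

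The note allowing later additions leaves the remedy open. The study is open-label, the interim analysis of Cohorts 1-4 and 8 was done before this SAP was signed, and no rule says which agents qualify. An addition could therefore be decided with viral loads in view.

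**Working it through.** The SAP states no figure on this point, so there is none to reproduce. The check is a comparison of lists.

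**Step 1. Antiviral flags in Table 13-2 against Table 13-1**

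| Agent | Class flag in Table 13-2 | In Table 13-1? |
|---|---|---|
| Hydroxychloroquine | Experimental antiviral | Yes |
| Azithromycin | Experimental antiviral (also immune modulator, anti-inflammatory) | No |
| Ganciclovir | Experimental antiviral only | No |
| Potassium phosphate dibasic | Experimental antiviral (also immune modulator, anti-inflammatory) | No |
| Potassium phosphate dibasic with sodium phosphate | Experimental antiviral (also immune modulator, anti-inflammatory) | No |
| Plasma | Antiviral antibody therapy only | No |

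Six agents carry one of the two flags. One is in Table 13-1 and five are not.

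**Step 2. Agents named in Section 4.3 against Table 13-1**

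Lopinavir/ritonavir and chloroquine are in Table 13-1. Interferon is not, and it is not in Table 13-2 either. One of three is missing.

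**Step 3. How far each flag can be trusted**

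The two potassium phosphate rows carry the same three positive flags as azithromycin. Either that grouping is intended or the rows are wrong; the SAP does not say. This makes the experimental antiviral column weak evidence for azithromycin, whose pattern is identical. It weakens the case for ganciclovir less, since its only flag is the antiviral one. Plasma is unaffected, because its flag is in a different column. Interferon does not depend on Table 13-2 at all.

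**Step 4. Possible size (illustration on assumed inputs)**

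Suppose *k* of *n* participants contribute samples taken under an unlisted agent, and that agent adds *d* log10 copies/mL of decline. The cohort mean change then shifts by (*k*/*n*) × *d*.

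- From the SAP: *n* = 12 per cohort in Cohorts 1-4.
- Assumed, because the SAP gives neither: *k* from 1 to 4, *d* from 0.25 to 1.0.
- Lower end: (1/12) × 0.25 = 0.02.
- Upper end: (4/12) × 1.0 = 0.33.

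One participant is 1/12 = 8.3% of a cohort. Within a single sample type *n* may be below 12, and the share is then larger.

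**The case against.** **The list is open.** Table 13-1 can be extended before data finalization. That softens the point. It does not settle it, because no criterion is given, and plasma, ganciclovir and azithromycin were already classed in the same appendix when the SAP was signed.

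**The tables do different jobs.** Table 13-1 drives an exclusion, while Table 13-2 groups medications for a descriptive summary. A flag there does not assert an effect on SARS-CoV-2 viral load, and a shorter exclusion list could be deliberate. This is fair, but the SAP gives no reason for the difference, and Section 7.4.3 confuses the two tables.

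**The flags are not all reliable.** The potassium phosphate rows show this, and the objection stands for azithromycin. That agent should not be moved into the main exclusion on the strength of its flag.

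**The analysis is secondary and descriptive.** No formal testing is planned, and without a comparator even a complete list would not separate the drug's effect from natural viral decline. This stands and limits the consequence.

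**Two stronger readings are not supported.** A reader might infer that the reported viral-load change does contain the effect of other antivirals. The SAP gives no use counts, so this depends on participants receiving such agents, having later samples, and the agents lowering viral load. A reader might also infer that this exclusion is the only safeguard. It is not: Section 3.7 removes participants with prior intravenous remdesivir, Section 4.3 lists anyone who took prohibited agents (interferon among them), and Section 7.4.3 tabulates COVID-19 medications by class and cohort. Those tabulations show co-exposure, but they do not remove the affected samples.

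**Conclusion.** The inconsistency is established from the SAP alone: Table 13-1 omits plasma, ganciclovir, azithromycin and interferon, each of which the SAP elsewhere gives an antiviral label. The evidence is strongest for plasma and for interferon, somewhat weaker for ganciclovir, and weakest for azithromycin.

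The effect on results is conditional and its size unknown. The range of 0.02 to 0.33 log10 copies/mL rests entirely on assumed numbers of participants and assumed added decline, and only shows what would follow if they held. The antiviral labels are the SAP's; nothing here claims that these agents are effective against SARS-CoV-2.

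The point merits correction because it concerns a stated secondary objective in small cohorts and the repair is cheap.

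**What to change.** Before database finalization:

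1. Add plasma, ganciclovir and interferon to Table 13-1 (7 + 3 = 10 entries), so that the exclusion covers the antiviral antibody class and the direct antivirals that the SAP names.
2. Check the two potassium phosphate rows in Table 13-2, and correct them if wrong, before any flag in that table drives a rule.
3. For azithromycin, specify now, however common its use proves to be, that viral load is shown both with and without samples taken on or after it. A rule that depends on observed use would be data-driven.
4. State a class-based criterion for any later addition to Table 13-1, applied without reference to viral-load results.
5. Correct Section 7.4.3 to cite Table 13-2 for the categories.

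The cost is an edit to two appendix tables and one cross-reference, a programming flag, and one additional viral-load display. The real downside is that some samples are lost from small cohorts already divided among four sample types.

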1.3. Sample Size and Power

The total sample size will be at least 52 participants.

Twelve (12) participants for each cohort (Cohorts 1-4) will be enrolled in this study. Pharmacokinetic data from these participants will provide >99% power for each cohort to conclude exposure equivalence of RDV AUC_{tau} in adolescents and children vs. 25 healthy adult participants in GS-US-399-5505 study (see Table 1-2) using two one-sided tests with each performed at an alpha level of 0.05. In this power analysis, it is assumed that the expected geometric mean ratio of AUC_{tau} between the adolescents and children group vs. the adult group is equal to 1, the inter-participant standard deviation (SD) (natural log scale) of AUC_{tau} is 0.18, and the equivalency boundary is 70% to 143%.

Meanwhile, twelve (12) participants from each cohort (Cohorts 1-4) will also provide >99% power to conclude exposure equivalence of RDV C_{max} in adolescents and children, compared to 26 healthy adult participants in GS-US-399-5505 study (see Table 1-2), assuming the expected geometric mean ratio of C_{max} between the adolescents and children group and the adult group is equal to 1, the inter-participant SD (natural log scale) of C_{max} is 0.19, and the equivalency boundary is 70% to 143%.

Sample size and power calculations were made using the software package nQuery Advisor(R) Version 8.5.

Table 1-2. Remdesivir, Nucleoside Metabolite GS-441524, and GS-704277 Plasma PK Parameters by Dose Following 30-Minute IV Infusion(s) of Remdesivir in Healthy Adult Participants in GS-US-399-5505

Study	GS-US-399-5505			
	Multiple RDV Dose (100mg)			
PK Parameter ^a		Day 5 and 10		
		$N = 26^{b}$		
Plasma RDV	Remdesivir	GS-441524 Metabolite	GS-704277 Metabolite	
C _{max} (ng/mL)	2228.8 (19.2)	145.0 (19.3)	245.5 (33.9)	
C _{tau} (ng/mL)		69.2 (18.2)		
C _{last} (ng/mL)	8.1 (46.9)	12.2 (50.0)	3.9 (27.5)	
T _{max} (h)	0.68 (0.25, 0.75)	1.51 (1.50, 2.00)	0.75 (0.75, 0.78)	
T _{last} (h)	4.00 (4.00, 4.02)	96.00 (96.00, 96.00)	8.00 (8.00, 8.00)	
t _{1/2} (h) ^d	0.96 (0.86, 1.08)	27.36 (25.29, 30.32)	1.23 (1.15, 1.38)	
AUC _{last} (h·ng/mL)	1562.8 (17.0)	4189.3 (17.7)	454.4 (31.8)	
AUC _{tau} (h·ng/mL)	1585.3 (16.6)	2229.2 (18.4)	461.5 (31.4)	
CL _{ss} (mL/h)	65068.7 (19.8)			
V _z (mL)	92557.2 (29.5)			

% CV = percentage coefficient of variation; IV = intravenous; PK = pharmacokinetic; Q1 = first quartile; Q3 = third quartile; $RDV = remdesivir (GS-5734^{TM})$

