3.1.2. Full Analysis Set

The Full Analysis Set (FAS) includes all enrolled participants who received at least 1 dose of study drug. This is the primary analysis set for efficacy analyses.

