3.1.3. Safety Analysis Set

The Safety Analysis Set includes all enrolled participants who received at least 1 dose of study drug. This is the primary analysis set for safety analyses.

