3.1.4. Pharmacokinetic Analysis Set

The RDV PK analysis set includes all enrolled participants who received at least 1 dose of RDV and for whom PK concentrations of RDV are available.

The SBECD PK analysis set includes all enrolled participants who received at least 1 dose of RDV and for whom PK concentrations of SBECD are available.

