3.8. Analysis Visit Windows

3.8.1. Definition of Study Day

Study day will be calculated from the first dosing date of study drug and derived as follows:

- For postdose Study days: Assessment Date First Dosing Date + 1
- For days prior to the first dose: Assessment Date First Dosing Date

Therefore, Study Day 1/ First Dose Date is the day of first dose of study drug administration, as recorded on the Study Drug Administration eCRF.

Last Dose Date is defined as the maximum, nonmissing, nonzero dose end date of treatment recorded on the Study Drug Administration eCRF form with "Study Drug Permanently Withdrawn" box checked for participants who prematurely discontinued or completed study drug according to the Study Drug Completion eCRF. Refer to Section 12 for missing date imputation, if necessary.

Last Study Date is the latest of the study drug start dates and end dates, the clinic visit dates, and the laboratory visit dates, including the 30-day follow-up visit date, for participants who prematurely discontinued study according to the Study Completion eCRF.

Baseline value is defined as the last nonmissing value obtained on or prior to the first dose date (and time, if available) unless otherwise specified.

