4.2. Extent of Study Drug Exposure and Adherence

Extent of exposure to study drug will be examined by summarizing the number of doses received by cohort and overall total for the Safety Analysis Set.

A by-participant listing of study drug administration will be provided by subject ID number (in ascending order) and visit (in chronological order).

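### Children given IV remdesivir before enrolment are removed from the viral-load analysis only; they remain unmarked in the GS-441524 and clinical-improvement summaries

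*SAP*

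**What the plan says.** SAP section 3.7 has one rule for children already treated with the drug: "For participants who had received IV RDV prior to the enrollment of this study, their viral loads will be excluded from the analysis". It gives no reason and does not extend the rule to any other endpoint.

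The analysis sets do not mention prior treatment:
- Section 3.1.4: "The RDV PK analysis set includes all enrolled participants who received at least 1 dose of RDV", provided that RDV concentrations are available.
- Section 3.1.2: "The Full Analysis Set (FAS) includes all enrolled participants who received at least 1 dose of study drug".
- Section 3.1.3 defines the Safety Analysis Set in the same terms.

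Section 3.6.2 keeps all data unless another rule applies. Section 8.2.1 includes everyone with concentration data in the concentration summaries. Sections 3.3 and 3.4 plan no covariates or subgroups for efficacy and safety. Section 7.4.1 gives no summary of prior medications, and section 7.4.2 provides only a by-participant listing.

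The time origin is in section 3.8.1: "Study day will be calculated from the first dosing date of study drug". Baseline is the last value at or before that dose. The ordinal-scale and PEWS endpoints in section 6.2 are built on this baseline and on Study Day.

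**The concern.** The existence of the rule shows that the plan allows for children who enter already on IV remdesivir. Prior dosing matters for two other groups of summaries.

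1. **PK, a primary objective.** GS-441524 is cleared slowly enough for metabolite from a dose given the day before enrolment to be present at the planned Day 2 and Day 3 samples. Table 8-1 also lists a GS-441524 AUC over the first 24 hours after the loading dose. In a pre-treated child, Study Day 1 is not the first dose, so that parameter does not measure what its label says.
2. **Clinical improvement, a secondary objective.** The baseline ordinal and PEWS scores of a pre-treated child are on-treatment values, and Study Day 1 falls after treatment began.

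No planned table would show how many children this concerns, so a reader of the study report could not judge whether it matters.

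**Working it through.** **The plan's own figure.** Section 1.3 claims power above 99% for parent RDV in each of Cohorts 1-4. I used two one-sided tests on the log scale at 0.05 each, a ratio of 1 and limits of 70% and 143%. For AUCtau (12 v 25, SD 0.18) power is 99.99%; for Cmax (12 v 26, SD 0.19) it is 99.97%. The claim reproduces.

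**Which analytes carry over.** Inputs are the adult median half-lives in Table 1-2. The fraction left 24 h after a dose is 2^(-24/half-life).

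| Analyte | Half-life (h) | Left at 24 h |
|---|---|---|
| RDV | 0.96 | 0.000003% |
| GS-704277 | 1.23 | 0.0001% |
| GS-441524 | 27.36 | 54% |

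Only GS-441524 matters. Its residue is 30% at 48 h, 16% at 72 h and 9% at 96 h.

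**Size for GS-441524.** Assumptions: single-exponential decay, linear superposition, the adult half-life, a Day 1 dose twice the daily dose (the ratio in every legible row of Table 1-1), and one loading-size dose 24 h before Study Day 1. Let r = 2^(-24/27.36) = 0.544, and count in maintenance-dose units.

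- Day 1 interval: carry-over 2r, study dose 2. Ratio = r = 0.544, so 54% too high.
- Before the Day 3 infusion: carry-over 2r³ = 0.323; study doses 2r² + r = 1.137. Ratio = 0.323/1.137 = 0.284, so 28% too high. With half-lives of 25.29 h and 30.32 h (the quartiles) it is 26% and 31%.
- Day 5 interval: carry-over 2r⁵ = 0.096; study doses 2r⁴ + r³ + r² + r + 1 = 2.18. Ratio = 0.044, so 4% too high.

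A maintenance-size prior dose halves each figure: 27%, 14% and 2%. Each further day between the prior dose and Day 1 multiplies the excess by 0.544. The pre-Day 3 excess of 28% at 24 h therefore becomes about 15% at 48 h and 8% at 72 h.

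**Effect on a cohort summary.** For the geometric mean of the pre-Day 3 level:
- One child in 12: 1.284^(1/12) = 1.021, about 2%.
- Three in 12: 1.284^(3/12) = 1.064, about 6%.
- One in four, the minimum planned for Cohort 5: also 1.284^(1/4) = 1.064, though the adult half-life is a weaker assumption in neonates.

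For the loading-dose AUC, one child in 12 gives 1.544^(1/12) = 1.037, about 4%.

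**Cost of leaving flagged children out.** Even for parent RDV, where exclusion is not needed, a cohort of 10 keeps power at 99.96% (AUCtau) and 99.9% (Cmax). A cohort of 8 keeps 99.8% and 99.6%.

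**Clinical improvement.** No size can be calculated. The number of pre-study dosing days is not given, and its effect on the baseline score is unknown.

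**The case against.** The strongest reply is that materiality is not shown. The SAP gives neither the number of pre-treated children nor the interval since their last dose, and the protocol, which is not at hand, may restrict prior use. Table 13-2 lists remdesivir among other COVID-19 medications, but section 7.4.3 limits that grouping to use from the first study dose onward, so it does not establish prior use. This stands, and it is a reason to report the count.

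Second, every GS-441524 boxplot in section 8.2.1 uses steady-state parameters, where carry-over is about 4% by Day 5. The SAP does not say how parameters are derived from sparse samples, and a derivation using the full dosing history would account for pre-study doses. This stands too. What remains is the Day 2-3 concentrations and the loading-dose AUC.

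Third, a 2% shift in a cohort geometric mean is small against a standard error of about 5% (adult CV 18.4%, and 18.4/√12 = 5.3). That is correct for one child in 12.

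Fourth, by-participant listings of medications, concentrations and PK parameters are planned, so a reader could trace these children. This helps, but a listing does not correct a pooled summary.

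A reader might infer more than the SAP supports:
- That treatment-emergent laboratory abnormalities are under-counted. An elevation already present at baseline could be missed, but one caused by a pre-study dose and first seen after Day 1 would be counted. The liver table in section 7.2.3 uses absolute multiples of the upper limit of normal. The net direction is unknown.
- That time to improvement is shortened. The clock starts late, but a child who has already improved has less room to gain a point, and one still needing treatment may be a slow responder.
- That counting only study doses in section 4.2 is a fault. That section concerns study-drug exposure, so the count is proper.
- That the section 3.7 rule concedes the baseline is invalid. The SAP gives no reason for the rule.

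**Conclusion.** The concern holds in a limited form. The SAP removes pre-treated children from the viral-load analysis and otherwise leaves them unmarked, so GS-441524 carried over from earlier doses is pooled into a primary-objective summary, and clinical improvement is measured from an on-treatment baseline.

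For an affected child, the GS-441524 excess could be about 54% on Day 1, 28% before the Day 3 infusion and 4% by Day 5. This rests on the adult half-life, single-exponential superposition and a loading-size dose 24 h earlier. It is smaller with a lower prior dose, a longer gap, or a derivation that uses the full dosing history. The effect on a cohort mean is a few per cent unless several children in a cohort were pre-treated.

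Parent RDV, GS-704277 and the power claim are untouched. Any effect on clinical or safety endpoints has no established direction. The point merits a modest change to the plan and does not call the study's conclusions into question.

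**What to change.** - Flag prior IV remdesivir, with number of doses and date of last dose where recorded, from the medication records already collected. The section 3.7 rule requires these children to be identified anyway.
- Report the number flagged by cohort and overall.
- Present GS-441524 concentrations and parameters with and without flagged children, or state that pre-study doses enter the dosing history used to derive the parameters.
- Repeat the time-to-improvement and recovery summaries without flagged children, as a sensitivity display.
- Keep every dosed child in the safety tables, and keep flagged children in the RDV and GS-704277 summaries.

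The cost is a few sentences in the SAP, one derived flag, a few extra tables and a slightly smaller n in the restricted ones. No new data collection should be needed.
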